Data Entry Requirements: All data will be coded by the research assistant prior to entry. The research assistants will maintain a log of any reviewed data issues so that future occurrences of problems will be handled in the same manner. The data entry system (REDCap) will require a login identification and password to gain access to the data. When appropriate, validation and range rules will be applied to the actual entry fields. Only the research assistants will be able to view the data in its raw state. All other authorized personnel (i.e. the PI, statistician and Data Safety Officer) will view data via forms and reports created by the research assistants.

Audit/Verification of Entered Data:

Primary Outcome Data: Data designated as primary outcome date (i.e., presence or absence of 30d readmission) will be subject to a 100% cross-reference check with original hard copies. This audit must have an error rate less than 0.5%. If the verification fails the audit, all data will be re-entered, the original computer files discarded, and the newly re-entered data audited. This process will continue until the audit no longer exceeds the maximum allowable error rate. All audits will be supervised and documented by the study's research assistant.

All Other Information: All other entered information will be subject to a 20% sample that will be cross-referenced with the original paper copy. This audit must have an error rate less than 0.5%. If the sample fails the audit, all data will be verified against the paper originals. If the error rate of the complete audit is greater than 0.5%, all data will be re-entered, the original computer files discarded, and the newly re-entered data audited. This process will continue until the audit no longer exceeds the maximum allowable error rate. At the discretion of the PI, the full audit may be omitted in favor of a complete re-entry of the original paper data. All audits will be supervised and documented by the research assistant.

Storage of Data: Data collected on paper from research participants will be placed in a locked file cabinet in the locked GCRC office. The destruction date of paper files will be at least 7 years from the termination of the study and will be authorized only by the PI. Electronic data will not include personal identifiers other than the unique study ID. Audio files for the in-depth interviews will be stored on the Research Specialist's password-protected computer and erased from the digital recorder after storage. All data will remain confidential. Access to

research and confidential records will be limited to trained clinical investigators and research coordinators.

Access to Cleaned Computer Data: Once the study is complete and data have been collected, entered, and passed the audit process, the Research Specialist will make the data available to the PI and anyone he designates. Only the PI can give permission for the release of aggregated study data. No confidential information may be released without the expressed written consent of the study participants. Only copies of the finalized, aggregated data will be released so that original data can remain confidential.

i) Confidentiality

Only trained research staff will have access to individually identifiable information under supervision of the PI. Staff will be trained to collect data for the study and maintain participants' confidentiality. Printed materials with identifiable participant information will be stored in a locked filing cabinet in the GCRC. The destruction date of paper files will be at least 7 years from the termination of the study and will be authorized only by the PI. Electronic data will be entered into REDCap, which requires a login identification and password to gain access. Electronic data will not include personal identifiers other than the unique study ID. Audio files for the in-depth interviews will be stored on the Research Specialist's password-protected computer and erased from the digital recorder after storage.

Presentation of the study results at regional or scientific meetings or in publications will not identify the subjects.

j) Provisions to Monitor the Data to Ensure the Safety of subjects

All participants will be given unique study identifiers. Data with personally identifiable information will be stored securely on HIPAA-compliant TUH servers. Data exported for statistical analysis will be stripped of personal identifiers. Participants will be free to withdraw from the study at any time.

Phase A: To minimize the risk of hypoglycemia, only patients with uncontrolled diabetes according to an elevated A1c will have their diabetes therapy adjusted. Patients will be followed closely for 30 days after discharge with weekly phone calls, and glycemic control will be monitored. Patients discovered to have hypoglycemia or hyperglycemia will be referred for adjustment of their diabetes therapy by the PI, an Endocrinologist.

A Data Safety Officer (DSO) not otherwise directly involved with the research, a senior diabetologist and clinical investigator with inpatient diabetes research experience, [name] at the University of Colorado Denver, will review de-identified data every 3 months. Adverse events will be reported to the Temple Institutional Review Board and the NIH according to standard policy.

Readmission Pilot Trial

Phase B: Every effort will be made to ensure that all qualitative data are kept confidential. The digital audio files produced will be used only for the purpose of this study. They will be downloaded from the recording device and stored on a secure computer in the research assistant's private GCRC office. The audio files will be transcribed. In the transcript, each subject will be assigned an anonymous study identification number. The data file linking personal identifiers and study identification numbers will be stored separately from the transcript data. The files with the transcribed data will have no personal identifiers and will contain no information linking an individual participant with their study code. The DSO will not monitor Phase B because there is minimal risk involved with this phase.

The following procedures will be implemented to ensure data safety and adequate monitoring:

- The PI will monitor study progress on an on-going basis and ensure the protection of human subjects, including the safe and secure collection and storage of data. An annual review will include assessment of accrual, adverse events, and data management practices.
- All data linking subjects to de-identified information will be maintained in a password-protected, encrypted computer with access limited to only those research personnel with a reasonable need to have such information.
- Reporting Adverse Events
 - Definitions:
 - Adverse Event: Any medical problem that manifests during the course of the study, as a result of an assessment or an aspect of the study intervention.
 - Serious Adverse Event: An adverse event that is fatal or life-threatening, results in significant or persistent disability, or requires hospitalization.
 - Unexpected Serious Adverse Event: Any event that has not been described in the protocol or informed consent document.
 - Reporting Mechanisms
 - All adverse events will be discussed at weekly operations meetings and reported to the PI and IRB according to standard operating procedure.
 - Serious adverse events (expected and unexpected) will be reported to the PI immediately and to the IRB in writing within 1 business day.
 - The NIH procedure for Reporting Clinical Study Serious Adverse Events will be followed for the reporting of expected and unexpected serious adverse events to the study sponsor.
- The DSO will review the protocol and study procedures every 3 months to ensure that proper regulatory processes are followed during study execution. In this role, he will:

Readmission Pilot Trial

- Review all adverse events or complications related to the study and make recommendations for protocol changes if indicated.
- Assure scientific integrity of the study by providing regulatory oversight.
- Assure participants' confidentiality and informed consent by reviewing study procedures.
- Provide advice, as requested, on quality assurance measures.

k) Withdrawal of Subjects

Subjects may withdraw at will at any time. Subjects may be withdrawn from the trial at the discretion of the PI due to a safety concern, if judged non-compliant with trial procedures, or pregnancy during the primary follow-up period (30 days after discharge). For subjects in the intervention group, we will obtain permission to continue to collect data from the electronic medical record.

9) Risks to Subjects

The study involves low risk from interviews and the intervention, which entails education, coordination of care, and post-discharge support. A1c-based adjustment of diabetes therapy poses the usual risk of hypoglycemia associated with diabetes therapy. However, only patients with uncontrolled diabetes according to an elevated A1c will have their diabetes therapy adjusted. Patients will be followed closely for 30 days after discharge and glycemic control will be monitored. Because the study will only be using FDA-approved medicines and checking routine A1C blood tests, it is unlikely that costs will be more than if a doctor was managing the subject outside the study.

10) Potential Benefits to Subjects

Participants in the intervention may have a lower risk of readmission and improved glycemic control with 30 days of discharge.

11) Privacy and Confidentiality

The study will use PHI and a HIPAA Authorization has been submitted. Paper data collection records with personal identifiers will be stored in locked file cabinets. Electronic data will not include personal identifiers other than the unique study ID. Audio files for the in-depth interviews will be stored on the research assistant's password-protected computer and erased from the digital recorder after storage. Access to research and confidential records will be limited to clinical investigators and research coordinators. All data linking subjects to de-identified information will be maintained in a password-protected, encrypted computer with access limited to only those research personnel with a reasonable need to have such information. Staff will be trained to collect data for the study and maintain participants' confidentiality. Interviews with subjects will be conducted in private. Presentation of the study results at regional or scientific meetings or in publications will not identify subjects.

12) Compensation for Research-Related Injury

If study volunteers sustain injury as a result of their participation in this study, they will be advised to seek immediate medical attention. However, there is no commitment by Temple University, Temple University Health System or its subsidiaries to provide monetary compensation or free medical care in the event of a study-related injury. The study volunteers have not waived any of their legal rights which they would otherwise have as a participant in an investigational study.

13) Economic Burden to Subjects

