a) Recruitment Methods

We will recruit study subjects as follows:

1. We will review a daily computer-generated admission log of patients admitted to medical-surgical units at TUH who have been ordered for routine glucose testing. This captures most patients with recognized diabetes.
2. We will review the medical chart of patients on the admission log to determine potential eligibility. We request a waiver of consent and HIPAA to identify candidates. We will access only the minimum data needed to obtain this information.
3. We will request permission to approach the potential subject about the study from a physician on the primary team providing hospital care.
4. Study participants will be provided \$50 after 30 days of follow-up has been completed and outcomes have been assessed. Subjects who also provide an in-depth interview after the follow-up period will be given another \$50.

b) Inclusion and Exclusion Criteria

Screening for eligibility will be performed by chart review and brief history of the potential subject.

Inclusion criteria

1. Diabetes, defined by pre-admission use of a diabetes-specific medication and/or documentation of the diagnosis in the medical record.
2. Age 18 years or older at the time of admission
3. Admission to a non-critical care unit

Exclusion Criteria:

1. Female subjects who are pregnant and/or admitted to an obstetric service

Readmission Pilot Trial

2. Binge drinking (5 or more alcoholic drinks for males or 4 or more alcoholic drinks for females on the same day) or drug abuse within 3 months before admission
3. Receiving palliative care during the hospitalization
4. Participation in another readmission risk reduction program
5. Inpatient death
6. Planned or actual transfer to another hospital or subacute facility
7. Discharge to hospice or a long-term care facility
8. Discharge by signing out against medical advice
9. Discharge expected within 12 hours or admission to a short-stay unit
10. Lack of access to a phone
11. Living more than 30 miles away from TUH
12. Mental condition rendering the subject unable to understand the nature, scope, and possible consequences of the study
13. A1c <5.7%
14. Inability to speak English

c) Local Number of Subjects

Up to 300 subjects will be enrolled locally across the following study groups: 60 subjects in the intervention group, 60 in the high-risk control group, and 180 in the low-risk control group.

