We estimate that 25% of screened patients will not meet eligibility criteria, which means that at least 300 patients will be screened.

d) Study Timelines

Subjects will be enrolled during their hospital stay and will participate in the study for 3 months following hospital discharge. The intervention will be delivered during the 4 weeks following discharge. Final assessment for outcomes will be performed at 3 months after discharge. We anticipate enrollment will occur between July and December of 2019. We estimate that primary analyses will be completed by June of 2020.

e) Study Endpoints

The primary outcome will be the number of initial hospital readmissions within 30 days of discharge. Secondary outcomes will also be assessed at 30 days of discharge unless otherwise specified. Secondary outcomes will include:

1. time to first readmission
2. number of emergency department (ED) visits
3. a composite of 30d readmissions and ED visits

Readmission Pilot Trial

4. number of primary care and specialist provider follow-up visits scheduled and attended
5. incidence of medication review or reconciliation post-discharge
6. cost of post-discharge care as a sum of ED visits, readmission, home health services, and outpatient provider visits
7. cost of the intervention
8. subject experience assessed by a brief questionnaire
9. self-monitored blood glucose levels and frequency of testing
10. change in well-being from baseline to 5 weeks after discharge as measured by the World Health Organization Well-Being Index (WHO-5).[43]
11. change in diabetes-related distress at 5 weeks after discharge as measured by the Problem Areas in Diabetes (PAID) scale.[44]
12. change in perceived social support at 5 weeks after discharge as measured by the Multidimensional Scale of Perceived Social Support (MSPSS).[45]
13. change in perceived stress at 5 weeks after discharge as measured by the perceived stress scale (PSS).[46]
14. change in diabetes knowledge at 5 weeks after discharge as measured by the Diabetes Knowledge Test (DKT2).[47]
15. change in A1c level from baseline to 3 months after the index discharge

f) Procedures Involved in the Human Research

After enrollment, subjects will be sorted into 2 groups based on the predicted risk of readmission by the DERRI: high risk and low risk (Figure 1).

[figure not shown]

Figure 1. Allocation of study participants

Low-risk group:

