Intervention protocol: The multifactorial intervention is based on strategies that reduced 30d readmissions in other populations, Temple’s successful readmission reduction program for heart failure patients (Temple Advantage), and the PI’s own preliminary studies. There are four components of the intervention: 1) patient-centered discharge education, 2) peri-discharge coordination of care, 3) A1c-based adjustment of diabetes therapy upon discharge, and 4) post-discharge support.

1) Patient-centered discharge education:

1a) *Standardized diabetes discharge instructions and education:* A Navigator will review instructions containing basic diet, activity, and diabetes-specific self-care guidance, as well as education on how to recognize and treat hypoglycemia and hyperglycemia (**Appendix Item 1**). These instructions are based on the model published by one of the PI’s mentors, [name], and others.[53] They also include a table that allows a provider to specify how and when insulin should be taken and discussion of the subject’s A1c level, of which many patients are not aware according to Preliminary studies. Lastly, patients who have not completed a formal diabetes education program in the past year will be referred to a Certified Diabetes Educator at the Temple Diabetes Center, an American Diabetes Association-certified outpatient diabetes education center.

1b) *Comprehensive discharge plan review:* Prior to discharge or soon after discharge, a Navigator will review the discharge plan with participants, including medications, reasons for and importance of follow-up appointments and testing, and how to reach post-hospital providers.

2) Peri-discharge coordination of care: Soon after discharge, a Navigator will assess and address barriers to following the discharge plan, including obtaining medications. A Navigator will confirm the scheduling of follow-up appointments and testing (including a visit with the primary care provider), help organize post-discharge services, assess barriers to keeping appointments, and confirm plans to attend follow-up appointments including transportation. In addition, a Navigator will assist subject with obtaining medications if needed. See **Appendix Item 2** for script.

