All data collected by the research team will be considered part of the participant's confidential record. Data collected on paper from research participants will be placed in a locked file cabinet in the GCRC within 24 hours. The destruction date of paper files will be at least 7 years from the termination of the study and will be authorized by the PI. Access to research and confidential records will be limited to clinical investigators and research coordinators.

h) Data Management

Statistical analysis: Distributions of the data will be assessed by descriptive statistical and graphical methods. To assess the randomization procedure, baseline values of all variables will be compared between the intervention and usual care group. Between-group differences for continuous variables will be compared using the Wilcoxon test. Proportions will be compared between groups using the chi-square test or exact tests when expected cell counts are less than 5. The primary outcome of 30d readmission rate will be compared between intervention and control groups with the chi-square test. Point estimates of 30d readmission rates will be obtained and presented with 95% confidence intervals. Time to readmission will be estimated by Kaplan-Meier curve and compared between groups by log-rank test. The composite of 30d readmission and ED visits will be compared by Cox regression model. Continuous secondary outcomes will be compared using Wilcoxon test. Categorical secondary outcomes will be compared using chi-square test. The primary analyses for all outcomes will be performed in the intention-to-treat (ITT) population. Secondary analyses for all outcomes will be performed in a per-protocol population restricted to subjects who complete at least one follow-up phone call. In addition, outcomes will be assessed for differences by the number of follow-up phone calls

Readmission Pilot Trial

completed (dose-response analysis). Lastly, all outcomes will be assessed in the ITT subgroup of subjects with a baseline A1c >7%. Statistical significance will be claimed at an alpha level of 0.05.

Power analysis: The sample size for Phase 2A was based on an expected drop-out and post-enrollment exclusion rate of 25% as well as the capacity of the research team. Because this is a pilot feasibility trial, the study is not powered to detect a difference in outcomes.

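### Exclusions settled only at discharge can fall after randomisation and are not reconciled with the intention-to-treat primary analysis

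*Protocol*

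**What the plan says.** Protocol section 8 b) gives one exclusion list for all subjects. Numbers 5 to 8 are "Inpatient death", "Planned or actual transfer to another hospital or subacute facility", "Discharge to hospice or a long-term care facility" and "Discharge by signing out against medical advice".

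Section 8 d) states: "Subjects will be enrolled during their hospital stay". Section 8 f) then sorts enrolled subjects by DERRI score and randomises the high-risk group 1:1. It gives no day or hour for randomisation.

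The abstract counts inpatient education among the parts of the intervention. In section 8 f), component 1b reads: "Prior to discharge or soon after discharge, a Navigator will review the discharge plan with participants". Component 3 has study endocrinologists set diabetes therapy at hospital discharge.

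Section 8 h) says, under the power analysis, "The sample size for Phase 2A was based on an expected drop-out and post-enrollment exclusion rate of 25" percent, and under the statistical analysis, "The primary analyses for all outcomes will be performed in the intention-to-treat (ITT) population". It does not define that population further.

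**The concern.** Some of these exclusions describe how the stay ended, so they cannot be applied when a patient is screened. If they are applied to subjects who already have an arm, randomised subjects leave the comparison because of something that happened after allocation. The protocol provides for exclusions after enrollment and names intention to treat as primary, but has no rule that joins the two.

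Staff and patients know the arm. Leaving against advice and the discharge destination are decisions that in-hospital education and discharge planning could affect, and usual care has no equivalent contact. The arms could therefore lose different kinds of patient. Efficacy is part of Aim 1, and a chi-square test of the primary outcome at 0.05 is planned, so the comparison will be read.

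**Working it through.** **Order of events.** Enrollment takes place in hospital, DERRI sorting follows, and randomisation comes after that. Inpatient education and therapy set at discharge can be delivered to one arm only if the arm is known by discharge. Randomisation before the end of the stay is therefore the natural reading. It is an inference, not a statement in the protocol.

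**Which exclusions can work at screening.**

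| Exclusion | Can it be judged before randomisation? |
|---|---|
| 5, inpatient death | No |
| 6, planned transfer | Yes |
| 6, actual transfer | No |
| 7, hospice or long-term care discharge | Often foreseeable; no if the destination changes |
| 8, leaving against advice | No |

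The list uses forecast wording elsewhere (*planned* in number 6, *expected* in number 9). The event wording of 5, 7, 8 and the second half of 6 therefore stands out.

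**The plan's own figure.** The protocol gives no evaluable target, event rate or effect size, so 60 per arm cannot be rebuilt. It is consistent with 45 evaluable per arm, since 45 / (1 − 0.25) = 60, but the 45 is inferred. The power statement names Phase 2A; I take this to be Phase A, the randomised trial. If the whole 25% were removed, 0.25 × 60 = 15 per arm would go, or 30 of 120. That is a ceiling, because the 25% includes drop-out and is not split.

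**Illustration, no true effect.** The risks and shares here are assumptions; the protocol gives none.
- n = 60 per arm
- f = share who would meet exclusions 5 to 8 = 0.10
- k = part of that share whom the intervention keeps from meeting an exclusion = 0.5
- readmission risk 0.20 in regular discharges and 0.40 in the would-be excluded

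All randomised subjects, either arm: (54 × 0.20 + 6 × 0.40) / 60 = 13.2 / 60 = 22.0%, so the true difference is zero.

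After exclusions:
- Intervention = [n(1 − f)(0.20) + nfk(0.40)] / [n(1 − f) + nfk] = (10.8 + 1.2) / (54 + 3) = 12 / 57 = 21.1%
- Usual care = 10.8 / 54 = 20.0%

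The false difference is 1.1 points against the intervention. If the intervention arm loses the whole stratum and usual care keeps half, the figures swap and favour the intervention.

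**Range.** Take an overall risk of 20% to 30%, excluded subjects with 1.5 to 2 times the risk of those kept, and the intervention arm excluding half as many of that stratum as usual care. With a 10% stratum, the false difference is 0.5 to 1.4 points. With strata from 5% to 25%, it is 0.3 to 3.4 points; the top end gives the whole 25% to these exclusions.

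**Against sampling error.** With 57 v 54 subjects and a 20% risk, the standard error of the difference is √[0.20 × 0.80 × (1/57 + 1/54)] = 7.6 points.

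**The case against.** The strongest reply is that the protocol never says randomised subjects leave the intention-to-treat set. It speaks of exclusion after enrollment, which precedes randomisation, and combines this with drop-out. An analysis plan that is not shown may define the set. Section 8 d) also places delivery of the intervention in the four weeks after discharge, and component 1b allows the plan review after discharge. This stands to the extent that the contradiction is conditional. It does not remove the point: exclusions 5 and 8 have no use at screening, the inpatient and at-discharge components need an arm by discharge, and the eligibility wording itself belongs to the protocol. An analysis plan also cannot recover outcomes that were never collected. Section 8 k) mentions continued access to records after withdrawal only for the intervention group.

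Four stronger readings are tempting but not supported:
- *All four exclusions can be met only after randomisation.* Planned transfer, and many hospice or long-term care discharges, can be foreseen.
- *Intention to treat is broken.* Removal from that set is inferred, not stated.
- *The bias could reach 5 points.* With the same assumed risks, f = 0.25 and k = 1 give 15 / 60 = 25.0% v 20.0%. That assigns all drop-out to these exclusions and has the intervention prevent every death, transfer, facility discharge and departure against advice, which is not credible.
- *The usual-care baseline rate for DERRI validation in Aim 2 is distorted.* Usual-care subjects have no contact with the intervention, so it cannot change who is excluded there. The same list applies to the low-risk cohort, so Aim 2 keeps one consistent population.

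It is also fair that no intervention component is aimed at these events, so losses may be nearly balanced.

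**Conclusion.** The point holds in a limited form. Exclusions 5 and 8, actual transfer in 6, and a late change of destination under 7 are settled only at the end of the stay. On the natural reading that is after randomisation. Removing randomised subjects for these events would contradict the stated primary analysis, and the protocol leaves this unresolved.

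The direction of any bias cannot be derived from the documents. Its size is probably small: about 1 point under the assumed risks with a 10% stratum and half retained, well inside the sampling error. The 25% is a ceiling and should not be read as the rate of these exclusions. Because Aim 1 is exploratory and the pilot is not powered for outcomes, this should be fixed but does not invalidate the trial. It is still worth fixing because the pilot is meant to guide a definitive trial, which could inherit these criteria.

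**What to change.** 1. Apply exclusions 6 to 8 only as what is planned or expected before randomisation, and drop the event wording for subjects already randomised.
2. Define the intention-to-treat set as all randomised subjects by assigned arm.
3. Follow everyone discharged alive for 30 days in both arms, whatever the discharge route, using the record review and 5-week call already planned under Data collection in section 8 f).
4. State which discharge starts the 30-day clock for a transferred subject.
5. Report inpatient deaths by arm. The outcome counted from discharge is undefined for them, so they are the only exception to the readmission denominator.
6. Restate the 25% as expected loss to follow-up or non-receipt of the intervention.

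Most of this is protocol wording, but items 4 and 5 are new rules. There are two costs. Subjects who leave early or go to a facility may receive little of the intervention and slightly dilute the effect. Outcome capture will be less complete for those moved to other institutions, where the hospital's own record may not show a readmission.

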We concluded that recurring reasons for admission of patients with diabetes are not being sufficiently addressed to prevent 30d readmission, and many patients do not get adequate discharge support. Furthermore, readmitted patients lack important knowledge about their diabetes and medications. The discharge process does not successfully communicate instructions to patients, and instructions often fail to address diabetes. These findings inform the planned intervention, and a similar qualitative method will be used to assess the intervention.

6) Setting of the Human Research

Potential subjects will be recruited at Temple University Hospital. All research procedures will be performed on the Temple Health Science Center Campus.

7) Resources Available to Conduct the Human Research

We estimate that in order to meet the desired final sample size, up to 300 subjects will need to be enrolled. Approximately 27,500 patients with diabetes are hospitalized at TUH annually. Assuming 25% of them will not meet eligibility criteria, there will be 20,600 potential subjects remaining over 1 year. We will therefore need to recruit 1.14% of potential subjects.

This work is being funded by an NIH K23, which covers 75% of the PI's total effort through February of 2019. A majority of the PI's research effort will be devoted to this project. One full-time Research Specialist ([name]) will support the study, including screening, consenting, and enrolling patients, entering data, and managing regulatory requirements. Our base of operation is at the General Clinical Research Center (GCRC), located at [name]. [name] will

Readmission Pilot Trial

supervise the following research assistants for screening, consenting, and enrolling patients, and entering data ([name], [name], [name], [name], and [name]). [name], one of the PI's colleagues in the Section of Endocrinology, will serve as a co-investigator to help with the clinical management of patients in the study.

In addition to the research specialist, a Nurse Navigator in the TUH Care Transitions Program ([name]) will deliver parts of the intervention, including diabetes education, coordination of care, and post-discharge follow-up.

All persons on the team administering the trial will be fully trained on the protocol and their study-related duties and functions. The Nurse Navigators have participated in protocol development.

8) Study Design

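### Do the screening floor of 300 and the 1.14% recruitment share, which do not follow from the protocol's own inputs, call for a change to the plan?

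*Protocol*

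**What the plan says.** Section 7 (Resources Available to Conduct the Human Research) sets out recruitment in four steps. It starts from the enrolment target: "We estimate that in order to meet the desired final sample size, up to 300 subjects will need to be enrolled". It gives the source population: "Approximately 27,500 patients with diabetes are hospitalized at TUH annually". It removes 25% as ineligible and says "there will be 20,600 potential subjects remaining over 1 year". It concludes: "We will therefore need to recruit 1.14% of potential subjects".

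Section 8c (Local Number of Subjects) repeats the target, "Up to 300 subjects will be enrolled locally across the following study groups", and divides it into "60 subjects in the intervention group, 60 in the high-risk control group, and 180 in the low-risk control group". The next sentence turns to screening: "We estimate that 25% of screened patients will not meet eligibility criteria, which means that at least 300 patients will be screened".

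Section 8d adds the recruitment window: "We anticipate enrollment will occur between July and December of 2019". The power analysis paragraph in section 8h bases the pilot's size on a separate 25% allowance for drop-out and exclusion after enrolment, and on what the team can handle. It says that the study is not powered to detect a difference in outcomes.

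**The concern.** Both sentences present a number as the result of a calculation, and in neither case does the calculation give that number. In section 8c the screening floor equals the enrolment ceiling, as if no screened patient were ineligible, although the same sentence expects a quarter to be. In section 7 the share is lower than the section's own numerator and denominator imply.

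Both slips make recruitment look easier than the inputs say. If screening effort had been budgeted on 300 patients, a team filling every place would have to screen at least a third more than planned. If the pool were tight, an understated share could hide a recruitment problem. It is therefore reasonable to ask whether the trial's size, staffing or timetable rests on either figure.

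**Working it through.** **Inputs.** Enrolment up to 300 (sections 7 and 8c; 60 + 60 + 180 = 300). Ineligible share 25% (sections 7 and 8c). Annual admissions with diabetes 27,500 and potential subjects 20,600 (section 7). Stated results: at least 300 screened (8c) and 1.14% (7).

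**Step 1: the pool.** 27,500 × (1 − 0.25) = 20,625. The stated 20,600 is this figure rounded, so this step reproduces.

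**Step 2: the recruitment share.** Share = enrolled / pool = 300 / 20,600 = 1.46% (1.45% with the unrounded 20,625). The stated 1.14% does not reproduce. Other pairings of the protocol's figures also miss it:

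| Pairing | Share |
|---|---|
| 300 / 27,500 | 1.09% |
| 225 / 20,600 | 1.09% |
| 400 / 27,500 | 1.45% |
| 400 / 20,600 | 1.94% |

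Working backwards, 0.0114 × 20,600 ≈ 235 subjects, a number the protocol does not contain. The gap is 1.46 − 1.14 = 0.32 percentage points.

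**Step 3: the number screened.** Screened = enrolled / (1 − ineligible share) = 300 / 0.75 = 400. This assumes that all 300 places are filled, that ineligibility is established before enrolment, and that every eligible patient consents; refusals would raise it. The common mistake of multiplying up instead, 300 × 1.25 = 375, does not give 300 either. Read the other way, 300 screened gives 300 × 0.75 = 225 eligible. The gap at full enrolment is 400 − 300 = 100 patients.

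**Step 4: does anything depend on these figures?**
- *Sample size.* The rationale in section 8h uses the post-enrolment loss allowance and team capacity. Neither 1.14% nor 300 screened appears in it.
- *Screening procedure.* Under section 8a, staff review a daily computer-generated admission log and then the charts. Screening continues with admissions; no quota of 300 ends it.
- *Adequacy of the pool.* 400 of 27,500 annual admissions is 1.45%. Section 8d plans about six months of enrolment. If admissions are assumed even over the year, the half-year pool is 20,600 / 2 = 10,300, and 300 / 10,300 = 2.9%. Section 7 openly labels its pool as annual, so this is a stress test and not a further error. The pool is ample either way.
- *Analyses.* The comparisons in section 8h are between randomized groups or subsets of them. None uses the number screened or the recruited share.

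**The case for a change.** The case for a correction is that both figures stand in complete sentences, both can be shown not to follow from the stated inputs, and both err towards less effort. In a pilot study, feasibility figures deserve care, and the repair is two short edits.

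Most of the arithmetic stands. The 1.14% has no defence. The 300 has a partial one. A floor of 300 is literally true, because nobody can enrol 300 without screening at least 300, and the enrolment figure is a ceiling that need not be reached. Some exclusions in section 8b, such as inpatient death or discharge against medical advice, may become known only after a patient has enrolled during the stay. Section 8h allows 25% for such losses, and 225 / 0.75 = 300 would make 300 an already inflated number. That reading is strained: the protocol states no target of 225, and section 8c applies its 25% to screened patients. It shows that 400 is conditional; it does not show that the sentence is sound.

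The appeal to feasibility does not stand. Aim 1 in section 4 concerns the feasibility, acceptability and efficacy of the intervention, not the screening workload.

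**Conclusion.** The slips are real but clerical. The recruitment share should read 1.46% of the annual pool, 0.32 points above the stated figure. The screening floor of 300 does not follow from the 25%; it would be 400 if all 300 places are filled, exclusions precede enrolment and nobody declines. Putting either right would leave the randomization, group sizes, endpoints, analyses and conclusions as they are, and the stated pool is many times larger than needed on any of these figures. An investigator working from the daily log will screen as many patients as enrolment requires, whatever section 8c says. No change to the plan is called for. The conclusion assumes that the stated 27,500 admissions and 25% ineligibility are roughly right; the document offers no means of checking them.
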